### 10.4 Statistical Analyses

The statistical analysis plan (SAP) will be finalized prior to primary endpoint DBL and it will include a more technical and detailed description of the statistical analyses described in this section. This section is a summary of the planned statistical analyses of the most important endpoints, including primary and key secondary endpoint.

A description of the participant population will be included in a statistical output report, including subgroups of age, gender, race, and other study specific populations and demographic characteristics. A description of participant disposition will also be included in the clinical study report.

#### **10.4.1 General Considerations**

RFS will be programmatically determined based on the disease recurrence date provided by the investigator and is defined as the time between the date of randomization and the first date of documented recurrence [REDACTED], or death (whatever the cause), [REDACTED]

**Table 10.4.1-1: Censoring Scheme for Definition of Recurrence-free Survival**

Event	Definition	Source
First documented recurrence	Time between randomization and first documented recurrence	Investigator
Death	Time between randomization and date of death	Investigator
Loss to follow-up	Time between randomization and last known date of contact	Investigator
Other	Time between randomization and other event (e.g., transfer to another study)	Investigator

The stratification factors for analysis are:

[figure not shown]
- AJCC v8 stage: Stage IIIA/IIIB vs Stage IIIC vs Stage IIID/IV (including all participants with mucosal melanoma, Stage III, Stage IVA, Stage IVB, and Stage IVC)
- Geographic region (USA/Canada/Australia vs Europe vs ROW)

DMFS, by investigator, is defined as the time between the date of randomization and the date of first distant metastasis or date of death (whatever the cause), whichever occurs first. [REDACTED]

OS is defined as the time between the date of randomization and the date of death. [REDACTED]

[REDACTED] OS will be followed continuously while participants are on the study drug and every 12 weeks via in-person or phone contact after participants discontinue the study drug.

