**Table 2-3: Follow-up Assessments (CA224098)**

Procedure	Follow-Up Visits 1 & 2 a	Long-term Follow-up b	Notes: c
Clinical Laboratory Assessments	X (see notes)		
To be performed at Follow-up Visit 1, repeat at Follow-up Visit 2 if study treatment-related toxicity persists.
 
Refer to Section 9.4.4, Clinical Safety Laboratory Assessments for the list of laboratory tests.
 
Laboratory toxicities (eg, suspected drug induced liver enzyme elevations) will be monitored during the follow-up phase, based on results from on-site/local labs, until all study drug related toxicities resolve, return to baseline, or are deemed irreversible.

Efficacy Surveillance			
Survival Status b	X	X (See Notes)	
During Long-term Follow-up, participant survival status is assessed every 12 weeks (<math>\pm</math> 14 days) by either a clinic visit or telephone contact, and must include documentation of subsequent therapy.
 
Participants will be followed until death, loss to follow-up, withdrawal of consent, conclusion of the study.
 
[REDACTED]

Body Imaging	See Notes		
Contrast-enhanced CT of the chest, abdomen, pelvis, and suspected sites of disease should occur every 12 weeks (<math>\pm</math> 7 days) for the first 2 years from randomization and every 26 weeks (<math>\pm</math> 14 days) beyond the Week 108 imaging time point until investigator assessed.
 
[REDACTED]
 
In cases of suspected lesions of the extremities, contrast-enhanced MRI may be substituted for contrast-enhanced CT.
 
For head and neck mucosal melanomas, contrast-enhanced MRI of head and neck is required at every time point for nodal surveillance.
 
Please refer to Appendix 9 for Germany-specific imaging language.

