### **8.1.2 Post-study Intervention Study Follow-up**

In this study, RFS is a key endpoint of the study. Post-study follow-up is of critical importance and is essential to preserving participant safety and the integrity of the study. Participants who discontinue study intervention must continue to be followed (in this study or a rollover study) for collection of outcome and/or survival follow-up data as required and in line with [Section 5.3](#) until death or the conclusion of the study.

BMS may request that survival data be collected on all randomized participants outside of the protocol defined window as defined in [Section 2](#). At the time of this request, each participant will be contacted to determine their survival status unless the participant has withdrawn consent for all contacts or is lost to follow-up.

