### **8.3 Lost to Follow-up**

The following actions must be taken if a participant fails to return to the clinic for a required study visit:

- All reasonable efforts must be made to locate participants to determine and report their ongoing status. This includes follow-up with persons authorized by the participant.
- Lost to follow-up is defined by the inability to reach the participant after a minimum of **three (3)** documented phone calls, faxes, or emails, as well as lack of response by participant to one (1) registered mail letter. All attempts should be documented in the participant's medical records.
- If it is determined that the participant has died, the site will use permissible local methods to obtain date and cause of death.
- If the investigator's use of third-party representative to assist in the follow-up portion of the study has been included in the participant's informed consent, then the investigator may use a Sponsor-retained third-party representative to assist site staff with obtaining the participant's contact information or other public vital status data necessary to complete the follow-up portion of the study.
- The site staff and representative will consult publicly available sources, such as public health registries and databases, in order to obtain updated contact information.
- If, after all attempts, the participant remains lost to follow-up, then the last known alive date as determined by the investigator should be reported and documented in the participant's medical records.

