## **9.1 Efficacy Assessments**

### **9.1.1 Efficacy Assessment for the Study**

Study evaluations will take place in accordance with [Section 2](#), Schedule of Activities. Surveillance for recurrence will be performed until investigator assessed [REDACTED]  
recurrence [REDACTED]

Contrast-enhanced CT of the chest, abdomen, pelvis, and all suspected sites of disease must be performed every 12 weeks ( $\pm$  7 days) from randomization for the first 2 years, and every 26 weeks ( $\pm$  14 days) beyond the Week 108 imaging time point thereafter until investigator assessed [REDACTED]

Imaging should be obtained anytime there is suspected disease. In cases of suspected lesions of the extremities, contrast-enhanced MRI may be substituted for contrast-enhanced CT. Please refer to [Appendix 9](#) for Germany-specific imaging language.

Participants with a history of brain metastasis or symptoms should have a surveillance MRI (without and with contrast) approximately every 12 weeks  $\pm$  7 days from randomization for the first 2 years and subsequently every 26 weeks ( $\pm$  14 days) beyond the Week 108 imaging time point thereafter until investigator assessed [REDACTED] recurrence [REDACTED]  
[REDACTED] or sooner if clinically indicated. Participants without history of brain metastases should have MRI if clinically indicated.

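### Does the RFS censoring table credit unassessed time as recurrence-free by dating lost participants at last contact?

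*Combined protocol and SAP*

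**What the plan says.** Section 10.4.1 states that "RFS will be programmatically determined based on the disease recurrence date provided by the investigator". It defines RFS as running from randomization to recurrence or death, and the sentence then breaks off into blacked-out text. Table 10.4.1-1 follows with four rows. For loss to follow-up it gives "Time between randomization and last known date of contact". For the row headed Other it gives "Time between randomization and other event (e.g., transfer to another study".

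Imaging and contact run on different schedules. Section 9.1.1 says "Contrast-enhanced CT of the chest, abdomen, pelvis, and all suspected sites of disease must be performed every 12 weeks" for the first two years, then every 26 weeks "beyond the Week 108 imaging time point thereafter until investigator assessed". In long-term follow-up, Table 2-3 has survival status checked every 12 weeks "by either a clinic visit or telephone contact".

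Section 8.3 counts a participant as lost only after at least three documented calls, faxes or emails and an unanswered registered letter; "then the last known alive date as determined by the investigator should be reported". Under Section 8.1.2, participants who stop study intervention "must continue to be followed (in this study or a rollover study") for outcome and survival data. Section 10.4 leaves the technical description of the analyses to the SAP.

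**The concern.** Recurrence is found mainly by scan, and a telephone call can establish little more than survival. If RFS time runs to the last call, the stretch between last scan and last call enters the risk set as recurrence-free time with little chance of a recurrence being documented. Kaplan-Meier RFS rates then rise, and if one arm loses more participants from scanning, the hazard ratio moves in that arm's favour. The transfer row seems to add to this by stopping the RFS clock although outcome data may still be collected in a rollover study.

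The stakes look considerable because RFS is the primary endpoint. Suppose 10% of the combination arm and 5% of the control arm stop scanning while contact runs to a 3-year cut-off, with 525 per arm. A simulation on those assumptions turned a true hazard ratio of 0.80 into 0.78, one of 1.00 into 0.975, and raised the rejection rate from about 0.61 to 0.69. Section 3.2.6 appears to make such an imbalance plausible: drug-related adverse events led to discontinuation in 14.6% versus 6.7% in the earlier advanced-melanoma trial.

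**Working it through.** **Can the table be read as the complete rule?** It is titled a censoring scheme, yet its columns are event, definition and source, with the investigator as source in every row. Nothing marks a row as event or censored. There is also no row for participants still followed without recurrence. Section 3.2 puts 3-year RFS on adjuvant checkpoint inhibitors at 45% to 58%, so about half of participants could be event-free at three years, and the table gives them no date. It therefore cannot be the whole scheme.

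The surroundings point the same way. The RFS definition is cut by a redaction where a censoring rule would naturally follow. The intercurrent-event detail in Table 10.4.1-2 is missing, and the Amendment 01 change entries for this table are blacked out. The public text is a program's reading of a redacted PDF, and elsewhere that reading describes redaction bars as content: Section 7.7.1.1 comes out as a bar chart. The two rows may be genuine, but they are weak evidence of the sponsor's rule.

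**Who falls in the loss-to-follow-up row?** Under Section 8.3, only someone who cannot be reached. A participant who declines scans but still answers calls is not lost, and no readable row dates them. The figures above with contact to cut-off (0.78, 0.975, 0.69) therefore model people outside the row. What remains is a participant who stops scanning, is reachable for a while, and is then lost.

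**What does the transfer row do?** It sets an RFS time at transfer. That shortens the time counted. It can credit unassessed time only between the last scan and the transfer. It might leave out later recurrences, which is a separate question of informative censoring, and it does not end follow-up, because Section 8.1.2 continues it.

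**How large is the remaining case?** The plan has no figure to reproduce here, since alpha, power, hazard ratio, events and dropout in Section 10.2 are blacked out. Inputs:

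- Control RFS of 70.5% and 62.6% at 12 and 24 months (Section 5.4.3), and 58% at 3 years (upper figure, Section 3.2).
- Yearly hazards: −ln(0.705) = 0.350; ln(0.705/0.626) = 0.119; ln(0.626/0.58) = 0.076.
- Scans every 12 weeks to Week 108, then every 26 weeks; 3-year cut-off; Cox model; 1,000,000 simulated per arm.
- Assumed: scan loss unrelated to recurrence, its 2-year rate, and how long contact outlasts scanning.

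| 2-year scan loss, combination vs control | Contact beyond scanning | True HR | HR, last scan | HR, last contact |
|---|---|---|---|---|
| 10% vs 10% | 52 weeks | 0.80 | 0.8045 | 0.8050 |
| 10% vs 5% | 0 weeks | 0.80 | 0.8072 | 0.8068 |
| 10% vs 5% | 26 weeks | 0.80 | 0.8031 | 0.7932 |
| 10% vs 5% | 52 weeks | 0.80 | 0.8052 | 0.7893 |
| 5% vs 10% | 26 weeks | 0.80 | 0.8044 | 0.8150 |
| 5% vs 10% | 52 weeks | 0.80 | 0.8047 | 0.8215 |
| 10% vs 5% | 52 weeks | 1.00 | 0.9972 | 0.9772 |
| 15% vs 5% | 52 weeks | 0.80 | 0.8050 | 0.7726 |
| 15% vs 5% | 52 weeks | 1.00 | 1.0009 | 0.9604 |

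With equal loss of 2% to 10%, the two datings never differ by as much as 0.001 in the hazard ratio. At 10% versus 5% and a true ratio of 0.80, the shift is 0.8031 − 0.7932 = 0.010 at 26 weeks and 0.8052 − 0.7893 = 0.016 at 52 weeks. At a true ratio of 1.00 and 52 weeks it is 0.9972 − 0.9772 = 0.020. The extreme 15% versus 5% case gives 0.032 and 0.041.

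With equal loss, control RFS at Week 108 rises by 0.2 to 0.8 points at 26 weeks (at 10% loss, 63.04% − 62.27% = 0.8) and by 0.2 to 1.2 points at 52 weeks (at 10% loss, 63.41% − 62.17% = 1.2). If contact ends with scanning, the mean gap from last scan to last contact is about 7.5 weeks and the rise is 0.0 points.

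**The case for a change.** The strongest case for the concern is that no readable text names the last disease assessment as the RFS censoring date, while a table titled as the censoring scheme names last contact. Section 8.3 asks sites for a last-known-alive date, which says nothing about recurrence. Section 9.1.4 requires cytology or histology for several kinds of lesion, which a call cannot supply. Someone who drops scans, answers calls for some months and is then lost does fall in the row, and the Kaplan-Meier curve is then slightly too high even with equal loss.

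Part of this stands. The readable text does not settle the censoring date, and it does not say how the transfer row fits with Section 8.1.2. But missing detail beside a redaction is not a wrong rule, and the harm to the comparison needs unequal loss from scanning, which is assumed. The 14.6% versus 6.7% figures describe stopping treatment in advanced disease. Here Section 9.1.2 keeps imaging on schedule when dosing is delayed or stopped, and the trial is double-blind.

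Nor is late contact blind to events. Table 2-3 requires subsequent therapy to be documented at these contacts, Section 9.1.2 collects unscheduled and outside scans, and deaths remain RFS events.

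**Conclusion.** The concern does not hold. It takes two rows of a visibly incomplete table as the full censoring rule for the primary endpoint, when the passage that would state the rule is blacked out and the detail is left to the SAP. Its main scenario lies outside the quoted row, and the transfer row does not produce the stated effect.

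Taken literally, the row would have no material effect on the hazard ratio under equal loss and would shift it by about 0.01 to 0.02 under a 5% versus 10% imbalance, in either direction depending on which arm loses more. The most extreme case run gave 0.03 to 0.04. These sizes rest on assumed loss rates, on contact outlasting scanning by 26 to 52 weeks, and on loss unrelated to recurrence. What remains is a point of reading: the table's wording should be checked against the source PDF, and the censoring date looked for in the unredacted text or SAP. No defect in the plan is shown.

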**Table 10.4.1-2: Definition of Estimands for Primary and Secondary Endpoints**

Objective	Endpoint	Estimand
Primary		
To compare the efficacy, as measured by RFS, provided by nivo + rela FDC vs nivolumab monotherapy in participants with completely resected Stage III/IV NED melanoma.	Recurrence or death per investigator	
Population: All randomized participants with completely resected Stage III/IV NED melanoma.
  
Treatment: Nivo + rela FDC compared to nivolumab monotherapy
 
Key Secondary Efficacy		
To compare the OS provided by nivo + rela FDC vs nivolumab monotherapy in participants with completely resected Stage III/IV NED melanoma.	OS	
Population: All randomized participants with completely resected Stage III/IV NED melanoma.
  
Treatment: Nivo + rela FDC compared to nivolumab monotherapy
 
Other Secondary Efficacy		
To assess the efficacy as measured by distant metastasis-free survival (DMFS), provided by nivo + rela FDC vs nivolumab monotherapy in participants with completely resected Stage III/IVA/IVB NED melanoma.	Distant recurrence or death per investigator	
Population: All randomized Stage III/IVA/IVB NED participants
 
Population level summary: 
 
Treatment: Nivo + rela FDC compared to nivolumab monotherapy
 

**Table 10.4.1-2: Definition of Estimands for Primary and Secondary Endpoints**

Objective	Endpoint	Estimand
		[REDACTED]
To compare PFS2 between nivo + rela FDC vs nivolumab monotherapy in randomized participants.	PFS2	
Population: All randomized participants
 
[REDACTED]
 
Treatment: Nivo + rela FDC compared to nivolumab monotherapy
 
[REDACTED]

Safety		
To assess safety and toxicity of nivo + rela FDC vs nivolumab monotherapy in participants with completely resected Stage III/IV NED melanoma.	Incidence and severity of AE, SAEs, IMAEs, drug-related AE/SAE, AEs leading to discontinuation, deaths, other select AEs and laboratory abnormalities.	
Population: Safety analysis population (defined in Section 10.3)
 
[REDACTED]
 
[REDACTED]
 
[REDACTED]
 
Treatment: Nivo + rela FDC compared to nivolumab monotherapy
 
[REDACTED]

Abbreviations: AE, adverse event; CI, confidence interval; DMFS, distant metastasis-free survival; FDC, fixed dose combination; NED, no evidence of disease; OS, overall survival; PFS2, progression-free survival 2; RFS, recurrence free survival; SAEs, serious adverse events; [REDACTED].

a [REDACTED]

### 10.4.2 Primary Endpoint(s)

Table 10.4.2-1: Primary Endpoints

Primary Endpoint	Description	Timeframe
Primary Efficacy		
Recurrence Free Survival (RFS)	Time from randomization to the first documentation of recurrence [REDACTED] or death due to any cause, whichever occurs first.	[REDACTED]

Table 10.4.2-2: Summary of Primary Endpoint Analysis

Endpoint	Statistical Analysis Methods
RFS as assessed by the investigator. RFS is defined as the time between the date of randomization and the first date of documented recurrence [REDACTED] or death due to any cause, whichever occurs first.	RFS distributions will be compared between treatment groups (nivo + rela FDC vs nivolumab monotherapy) [REDACTED] in all randomized population. [REDACTED] [REDACTED] [REDACTED]

Abbreviations:

FDC, fixed dose combination;

[REDACTED] RFS, recurrence-free survival.

**10.4.3 Secondary Endpoint(s)****Table 10.4.3-1: Secondary Efficacy Endpoints**

Secondary Endpoints	Description	Timeframe
Key Secondary Efficacy		
Overall Survival	Time from randomization date until death (whatever the cause)	[REDACTED]
Other Secondary Efficacy		
Distant metastasis-free survival	Time from date of randomization to the date of first distant metastasis or date of death (whatever the cause, whichever occurs first).	[REDACTED]

**Table 10.4.3-2: Summary of Secondary Endpoint Analysis**

Secondary Endpoints	Statistical Analysis Methods
Key Secondary	
OS is defined as the time between the date of randomization and the date of death (whatever the cause).	[REDACTED]
Other Secondary	
DMFS, by investigator, is defined as the time between the date of randomization and the date of first distant metastasis or date of death (whatever the cause), whichever occurs first.	[REDACTED]
PFS2 defined as time from randomization to second recurrence/objective disease progression on next-line systemic therapy per investigator, or death from any cause, whichever occurs first.	[REDACTED]

Abbreviations: [REDACTED] DMFS, distant metastasis free survival; FDC, fixed dose combination; [REDACTED] overall survival; PFS2, progression-free survival 2.

#### 10.4.3.1 Safety Analysis

Table 10.4.3.1-1: Safety Analysis

Safety Endpoint	Description	Timeframe
Safety		
Incidence and severity of AEs, SAEs, IMAEs, other select AEs, laboratory abnormalities, drug related AEs/SAEs, death	Incidence and severity (i.e. CTC grade) of AEs, SAEs, IMAEs, other select AEs, laboratory abnormalities, drug related AEs/SAEs, death	Up to 135 days after the last dose of study treatment
Incidence of AEs leading to discontinuation	Incidence and severity of AEs leading to discontinuation of study treatment	Up to discontinuation of study treatment

[figure not shown]
Abbreviations: AE, adverse event; CTC, Common Terminology Criteria; IMAEs, immune mediated adverse events; SAE, serious adverse event.

[figure not shown]
[REDACTED]  
[REDACTED]  
[REDACTED]

#### 10.4.5 Other Safety Analysis

All safety analyses will be performed using the Safety analysis population.

Endpoint	Statistical Analysis Methods
The Safety and tolerability objective will be measured by the incidence and severity of adverse events (AEs), serious adverse events (SAEs), and adverse events leading to discontinuation study drug, select AEs, immune-mediated AEs (IMAEs), other events of special interest (OESIs), deaths, and laboratory abnormalities in each arm.	All safety analyses will be performed using the safety analysis population. The frequency of deaths, adverse events (AEs), serious adverse events (SAEs), AEs leading to discontinuation of study drug, select AEs, immune-mediated AEs (IMAEs), other events of special interest (OESIs), and abnormalities in specific clinical laboratory assessments will be presented. The safety summaries will be presented by severity where applicable. Analyses will be conducted using the 30-day and/or 135-day safety window from day of last dose received. AEs will be coded using the most recent Medical Dictionary for Regulatory Activities (MedDRA) version available during the conduct of the study. AEs and laboratory values will be graded for severity according to the National Cancer Institute (NCI) Common Terminology Criteria for Adverse Events (CTCAE) version 5.0.

**12 APPENDICES**

**APPENDIX 1 ABBREVIATIONS AND TRADEMARKS**

Term	Definition
ADA	anti-drug antibodies
AE(s)	adverse event(s)
AIDS	acquired immunodeficiency syndrome
AJCC	American Joint Committee on Cancer
ALP	alkaline phosphatase
ALT	alanine aminotransferase
ART	antiretroviral therapy
AST	aspartate aminotransferase
AUC(TAU)	area under the plasma concentration-time curve over dosing interval
AxMP	auxiliary medical product
[REDACTED]	[REDACTED]
BICR	blinded independent central review
BMS	Bristol Myers Squibb
BRAF	B-RAF proto-oncogene
BUN	blood urea nitrogen
Cavgss	steady state average concentration
CBC	complete blood count
C	cycle
CD	cluster of differentiation
CFR	Code of Federal Regulations
cHL	classical Hodgkin's lymphoma
CI	confidence interval
CIOMS	Council for International Organizations of Medical Sciences
CL	clearance
CrCl	creatinine clearance
CLNR	nonrenal clearance
CLND	complete lymph node dissection
CLss	steady-state clearance
Cmax	maximum observed concentration

Term	Definition
CNS	central nervous system
COVID-19	coronavirus disease 2019
[REDACTED]	[REDACTED]
CRC	colorectal cancer
CrCl	creatinine clearance
CRF	case Report Form, paper or electronic (eCRF)
CSR	clinical study report
CT	computed tomography
CTAg	clinical trial agreement
CTCAE	common terminology criteria for adverse events
[REDACTED]	[REDACTED]
CTLA	cytotoxic T-lymphocyte-associated protein 4
CV%	coefficient of variation %
D	day
DAB	dabrafenib
dL	deciliter
DILI	drug induced liver injury
DLT	dose limiting toxicity
DMC	data monitoring committee
DMFS	distant metastasis-free survival
[REDACTED]	[REDACTED]
DRESS	drug reaction with eosinophilia and systemic symptoms
eCOA	electronic clinical outcome assessments
ECG(s)	electrocardiogram(s)
ECOG	Eastern Cooperative Oncology Group
eCRF	electronic Case Report Form
EC50	half-maximal effective concentration
eg	exempli gratia (for example)
eGFR	estimated glomerular filtration rate
EOI	end of infusion

Term	Definition
E-R	exposure-response
EUDAMED	European Databank on Medical Devices
FDA	Food and Drug Administration
FDC	Fixed-dose combination
FDG	fluorodeoxyglucose
FFR	Freedom From Relapse
FGL-1	fibrinogen-like protein 1
FSH	follicle stimulating hormone
ft3	free T3
ft4	free T4
FU	follow-up
GBS	Guillain-Barre Syndrome
GCP	Good Clinical Practice
GFR	glomerular filtration rate
GI	gastrointestinal
h	hour
HBsAg	hepatitis B virus surface antigen
HBV	hepatitis B virus
HCC	hepatocellular carcinoma
HCG	human chorionic gonadotropin
HCV	hepatitis C virus
H&E	hematoxylin & eosin
HIPAA	Health Insurance Portability and Accountability Act
HIV	Human Immunodeficiency Virus
HR	hazard ratio
HRQoL	health-related quality of life
HRT	hormone replacement therapy

Term	Definition
IA	interim analysis
IB	Investigator's Brochure
IC50	half-maximal inhibitory concentration
[REDACTED]	[REDACTED]
ICF	informed consent form
ICH	International Conference on Harmonisation
ICMJE	International Committee of Medical Journal Editors
IDO	indoleamine 2,3-dioxygenase
ie	id est (that is)
IEC	Independent Ethics Committee
[REDACTED]	[REDACTED]
[REDACTED]	[REDACTED]
IgG4	immunoglobulin G4
IHC	immunohistochemistry
IMAE	immune-mediated adverse event
IMG	immunogenicity
IP/IMP	investigational [medicinal] products
IND	Investigational New Drug Exemption
IO	immuno-oncology
IPI	ipilimumab
IUS	intrauterine hormone-releasing system
IRB	Institutional Review Board
IRT	Interactive Response Technology
IU	International Unit
IV	intravenous
kg	kilogram
K-M	Kaplan Meier
LAG-3	lymphocyte activation gene-3
LAM	lactational amenorrhea method
LD	longest diameter

Term	Definition
LDH	lactate dehydrogenase
LN	lymph node
MedDRA	Medical Dictionary for Regulatory Activities
MEK	mitogen-activated protein kinase
mg	milligram
MG	Myasthenia Gravis
MHC	major histocompatibility complex
min	minute
mL	milliliter
mmHg	millimeters of mercury
[REDACTED]	[REDACTED]
MMR	measles, mumps, rubella
[REDACTED]	[REDACTED]
MRI	magnetic resonance imaging
MSLT-II	Multicenter Selective Lymphadenectomy Trial
MSS	melanoma specific survival rate
MTD	maximum tolerated dose
µg	microgram
N	number of subjects or observations
N/A	not applicable
NCCN	National Comprehensive Cancer Network
NCT	National clinical trial number
NED	no evidence of disease
ng	nanogram
NGS	next generation sequencing
NIMP	non-investigational medicinal products
Nivo	nivolumab
NK	natural killer
[REDACTED]	[REDACTED]
NSAID	nonsteroidal anti-inflammatory drug

Term	Definition
NSCLC	non-small cell lung cancer
OESI	other events of special interest
ORR	objective response rate
OS	overall survival
[REDACTED]	[REDACTED]
PD-1	programmed death-1
PD-L1	programmed death ligand-1
PD-L2	programmed death ligand-2
PEMBRO	pembrolizumab
PET	positron emission tomography
PET-CT	positron emission tomography-computed tomography
PFS	progression-free survival
PFS2	progression-free survival 2
PK	pharmacokinetics
PPK	population pharmacokinetics
PRO	patient reported outcome
Q2W	every 2 weeks
Q3W	every 3 weeks
Q4W	every 4 weeks
[REDACTED]	[REDACTED]
R&D	Research and Development
RCC	renal cell carcinoma
Rela	relatlimab
RFS	recurrence free survival
[REDACTED]	[REDACTED]
RO	receptor occupancy
ROW	rest of the world
RT-PCR	reverse transcription polymerase chain reaction
SAE(s)	serious adverse event(s)
SARS-CoV-2	severe acute respiratory syndrome coronavirus 2

Term	Definition
SAP	statistical analysis plan
SAV	single agent vial
[REDACTED]	[REDACTED]
SCCHN	squamous cell carcinoma of the head and neck
SJS	Stevens-Johnson syndrome
SLN	sentinel lymph nodes
SLNB	sentinel lymph node biopsy
SOA	Schedule of Activities
SPSD	Site Process and Source Documentation
SUSAR	suspected, unexpected serious adverse reaction
T3	triiodothyronine
T4	thyroxine
TB	total bilirubin
T.Bili	total bilirubin
TEN	toxic epidermal necrolysis
[REDACTED]	[REDACTED]
TME	tumor microenvironment
TILs	tumor infiltrating lymphocytes
[REDACTED]	[REDACTED]
TNM	tumor/node/metastasis
[REDACTED]	[REDACTED]
TRAE	treatment-related adverse event
TRAM	trametinib
TSH	thyroid stimulating hormone
TSST	time to second subsequent therapy
tT3	total T3
tT4	total T4
ULN	upper limit of normal
USA	United States of America
USPI	United States Prescribing Information

Term	Definition
VAS	visual analog scale
Vss/F (or Vss)	apparent volume of distribution at steady state
Vz	Volume of distribution of terminal phase (if IV and if multi-exponential decline)
WES	whole exome sequencing
WOCBP	women of childbearing potential
WS	Worldwide patient safety

